4.8.3 Criteria for excluding cases

- ① Misdiagnosis and wrong acceptance;
- ② No post-medication record;
- ③ No medication at all.

4.9 Conditions for discontinuation of research

Research discontinuation means that clinical studies have not been completed as planned and all studies have been stopped halfway. The main purpose of the suspension of research is to protect the rights and interests of subjects, ensure the quality of research and avoid unnecessary economic losses.

(1) Serious safety problems occur in the study, and the study should be discontinued in time.

(2) The study found that the effect of drug treatment is too poor, even ineffective, and has no clinical value. The study should be discontinued, on the one hand, to avoid delaying the effective treatment of subjects, while avoiding unnecessary economic losses.

(3) It is difficult to evaluate the drug effect because of the major mistakes in the clinical research program. Or a well-designed program has significant deviations in its implementation, and it is difficult to evaluate the drug effect if it continues.

(4) The applicant requests suspension (e.g. financial reasons, management reasons, etc.).

(5) Drug administration departments should withdraw research, etc.

5. Dosage regimen

5.1 Administration method

The course of treatment was 14 weeks, including 2 weeks of introduction and 12 weeks of double blind treatment.

Introducing period: 2 weeks, time window (+2 days).

Introducing drug regimen: Both groups were given Xinnaoning capsule Simulator 3 capsules per time, 3 times per day, orally, after meals.

Course of treatment: 12 weeks, time window (+4 days).

Drug regimen for treatment period:

Test group: Xinnaoning capsule 3 capsules per time, 3 times per day, oral, after meals.

Control group: Xinnaoning capsule Simulator 3 tablets per time, 3 times per day, oral, after meals.

Basic treatment: During the introduction and treatment period, the experimental group and the control group could use antiplatelet drugs, angiotensin converting enzyme inhibitors (ACEI) or angiotensin II receptor antagonists (ARB), statins lipid-lowering drugs, calcium antagonists, beta-blockers, long-acting nitrates and other drugs without changing the original dosage. Nitroglycerin 0.5 mg can be administered sublingually, and the times and dosage of medication can be recorded in detail.

Sports regulations: 3-5 times a week, each lasting 30-40 minutes, 6.5-7.5 kilometers a week. See Annex 1 for details.

5.2 Pharmaceutical Information for Testing Drugs

(1) Introducing drugs: Xinnaoning capsule simulator, the production unit is Guizhou Jingcheng Pharmaceutical Co., Ltd. Specification: 0.45g for each tablet, 12 tablets for each board, batch number: 20171113 valid until August 2019.

(2) The experimental group drug: Xinnaoning Capsule, the production unit is Guizhou Jingcheng Pharmaceutical Co., Ltd. Specification: 0.45g for each tablet, 12 tablets for each board, drug batch number 20170916. It is valid until August 2019.

(3) Control group drug: Xinnaoning capsule simulator, the production unit is Guizhou Jingcheng Pharmaceutical Co., Ltd. Specification: 0.45g for each tablet, 12 tablets for each board, drug batch number: 20171113. It is valid until August 2019.

5.3 Pharmaceutical Packaging for Testing Drugs

There are corresponding drug numbers and labels attached to the test drugs. The test drugs and the control drugs are packed in the same package. Each large package contains three boxes. The package contains Xinnaoning capsule or Xinnaoning capsule placebo. Each package contains 28 + 4 days of dosage. The drug was packed independently during the introduction period, and the dosage of 14 + 2 days was included in the package. The contents of the label include batch approval number, drug number, drug name, function, taking method, storage condition, drug supplier, etc., and the words "for clinical research only".

5.4 Case allocation method

Randomization method was adopted, which was carried out according to the center. With the help of SAS 9.1.3 statistical software, the random arrangement (i.e. random coding table) of the treatment (test drug and control drug) received by 240 subjects was generated. According to the randomly determined drug number allocated by each hospital, each center allocates continuously coded drugs connected with each other. Random numbers are sealed in opaque envelopes and centralized managed by test centers.

Each center screens patients, and qualified persons are selected. Drug administrators distribute drugs one by one according to the order of each subject's visiting and drug number from small to large. Subjects were asked to take the remnant drugs back when prescribed visiting points were prescribed. Drug administrators should fill in the "test drug distribution and recovery record form" in time.

5.5 Dose selection and administration time

In this experiment, all subjects were given a uniform fixed dose, which remained unchanged during the experiment, i.e. during the experiment, the dosage should not be adjusted or the mode of administration should not be changed. If the adverse events necessarily changed or other reasons caused changes, detailed records and treatment according to excluded cases were made.

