4.8.2 Subjects withdraw spontaneously

According to the informed consent, the subjects have the right to withdraw from the study halfway, or they have not explicitly proposed to withdraw from the study, but no longer accept medication and testing and lost interviews, which also belongs to "withdrawal" (or "fall off"). The reasons for their withdrawal should be understood and recorded as far as possible. Such as: poor self-efficacy; intolerable to some adverse reactions; unable to continue to accept clinical research; economic factors; or missing interviews without explaining the reasons.

Whatever the reason, the case records should be kept for the withdrawal cases, and the final test results should be transferred to the final results. The efficacy and adverse reactions of the withdrawal cases should be analyzed by a full data set. All withdrawal cases should be filled in the case report form, the conclusion form and the reasons for withdrawal. In general, there are six kinds, namely, adverse events

(including adverse drug reactions and allergic reactions), lack of efficacy (deterioration or complications), violation of research programs, loss of interviews (including withdrawal of the subjects themselves), suspension of the applicant and others.

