10.1 Analytical Data Set

(1) Full Analysis Set (FAS): refers to the ideal set of subjects as close as possible to the principle of intentional analysis. The data set is derived from all randomized participants by eliminating the participants with the least and reasonable method.

(2) PPS: It is a subset of the total analysis set. These subjects are more compliant with the scheme. Compliance includes the following considerations, such as the treatment they received, the absence of major efficacy indicators, and the absence of major violations of the research scheme.

(3) Safety Data Set (SS): When evaluating safety and tolerance, the set of subjects used to aggregate is called Safety Data Set. Subjects who received at least one treatment after randomization were included in the safety analysis set.

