10.2.3 Statistical analysis content

(1) CDAS3.0 statistical software will be used for statistical analysis.

(2) The main therapeutic data set was FAS analysis population, and the therapeutic PPS population was also analyzed.

(3) Except for the superiority test of the main therapeutic indicators, all other statistical tests are carried out by bilateral test, and the difference of P value less than or equal to 0.05 will be considered statistically significant.

(4) The measurements of each visit in different treatment groups will be described by means of standard deviation. Compared with the baseline values at the time of admission, paired t-test was used to compare the differences between before and after admission. Variance analysis was used to compare the changes before and after treatment in each group.

(5) Frequency (constituent ratio) was used to describe the counting data of each visit in different treatment groups. 2 test or non-parametric test were used to test the changes before and after treatment in each group.

(6) Comparability analysis: Comparing demographic data and other basic value indicators to measure the comparability between the two groups.

(7) Compliance analysis: Compare the two groups of patients whether to use the research drugs on time and in quantity, not using the drugs prohibited in the program.

(8) Abscission analysis: χ^2 test will be used to compare the total abscission rate and the abscission rate due to adverse events in each group.

(9) Equilibrium analysis of basic values: using variance analysis or 2 test to compare demographic data and other basic value indicators to measure the two groups of equilibrium.

(10) Effectiveness analysis: PPS and FAS were used to analyze the main indicators and global indicators, and CMH test considering the central effect was used to analyze the efficacy of the two groups. The main effect indicators were selected to treat 12 weeks of angina symptoms, and the placebo was used as the control for statistical test.

(11) Analysis of factors affecting efficacy: If there are significant correlative factors affecting efficacy, these factors should be considered as covariance analysis or logistic regression analysis when comparing the efficacy of the two groups. Detailed list of combined medication is required.

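### Section 5.5 treats subjects whose dose changes as excluded cases without naming an analysis set, which conflicts with the exclusion list in 4.8.3 and the full analysis set in 10.1

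*Protocol*

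**What the plan says.** Section 5.5 of the protocol sets one fixed dose for all subjects and then deals with departures from it. When an adverse event or another reason leads to a change, "detailed records and treatment according to excluded cases were made". The rule covers adverse events and any other reason, and it names no analysis set.

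Four other places bear on the same subjects:

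- **Section 4.8.3** lists the grounds for excluding a case. There are three: "Misdiagnosis and wrong acceptance", no record after medication, and "No medication at all".
- **Section 4.8.2** covers subjects who withdraw, and gives intolerable adverse reactions as one example of a reason. It says "The efficacy and adverse reactions of the withdrawal cases should be analyzed by a full data set".
- **Section 10.1** says the FAS "refers to the ideal set of subjects as close as possible to the principle of intentional analysis", and adds: "The data set is derived from all randomized participants by eliminating the participants with the least and reasonable method". It places compliance and the treatment received under the per-protocol set (PPS). It puts every subject with at least one treatment after randomisation in the safety set (SS), with no exception for a changed dose.
- **Section 10.2.3**, item 2: "The main therapeutic data set was FAS analysis population", with the PPS analysed as well.

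**The concern.** Excluded cases are a listed category in this protocol, and 5.5 sends subjects to it on a ground that the list does not contain. A dose change happens after randomisation. When an adverse event causes it, it can depend on which treatment the subject received, and it may be related to outcome. Removing subjects on such an event gives up the comparability that randomisation provides. If the removal reached the FAS, it would affect the main efficacy comparison.

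The result is also inconsistent within the protocol. A subject who stops the study drug because of an adverse reaction is a withdrawal and stays in the full data set. A subject with the same reaction who continues on a changed dose is handled as excluded. Elsewhere the protocol keeps unfavourable courses in the analysis: 7.1.2 counts subjects who leave because of worsening after more than 4 weeks as non-curative cases, even in the PPS.

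**Working it through.** **Step 1. Follow one subject through the text.** Take a subject who is randomised, takes study drug, has records after treatment, and has the dose changed because of an adverse event.

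| Section | Status of this subject |
|---|---|
| 4.8.3, exclusion grounds | Correctly enrolled, has post-medication records, took drug: meets none of the three |
| 10.1, FAS | Randomised, with no stated reason for removal: in |
| 10.1, SS | At least one treatment: in |
| 10.1, PPS | May be out, because the treatment received is a PPS consideration |
| 4.8.2, had the subject stopped instead | Withdrawal: in the full data set |
| 5.5 | Handled as an excluded case, set not stated |

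Only the PPS row is compatible with 5.5, and 5.5 does not limit itself to the PPS.

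**Step 2. What the size could be.** The protocol has no figure for how often doses change, so there is nothing to reproduce on that point. The inputs available are the planning rates and group size in section 3.2: 67.5% effective on control, 84.3% on test, 120 per group. In whole subjects:

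- test: 0.843 × 120 = 101.2, taken as 101; 101/120 = 84.2%
- control: 0.675 × 120 = 81; 81/120 = 67.5%
- difference with nobody excluded: 16.7 points

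If an arm has N subjects and x responders, and k subjects are excluded of whom r responded, the analysed rate is (x − r)/(N − k). When r/k = x/N, the rate does not change and the bias is zero. The table takes the extreme r = 0 (only non-responders excluded). The numbers excluded are assumptions. Shifts are from unrounded values.

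| Excluded, test / control | Test | Control | Difference | Shift |
|---|---|---|---|---|
| 2 / 1 | 101/118 = 85.6% | 81/119 = 68.1% | 17.5 | +0.9 |
| 5 / 2 | 101/115 = 87.8% | 81/118 = 68.6% | 19.2 | +2.5 |
| 8 / 3 | 101/112 = 90.2% | 81/117 = 69.2% | 20.9 | +4.3 |
| 2 / 5 (reversed) | 101/118 = 85.6% | 81/115 = 70.4% | 15.2 | −1.5 |

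The last row shows that the sign depends on which arm loses more subjects.

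**Step 3. The same with no true effect.** Assume 67.5% effective in both arms, and a fraction e of the test arm only excluded. If those excluded respond at rate q, the apparent test rate is (0.675 − e·q)/(1 − e). The last column is a normal approximation for a two-sided 5% test of two proportions, ignoring centre, with 120 control subjects and 120(1 − e) test subjects.

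| e | Gain, q = 0 | Gain, q = 0.3375 | Gain, q = 0.675 | Chance of a false result favouring test, q = 0 (nominal 2.5%) |
|---|---|---|---|---|
| 2% | 1.4 | 0.7 | 0 | 4.2% |
| 5% | 3.6 | 1.8 | 0 | 8.5% |
| 10% | 7.5 | 3.8 | 0 | 23.6% |

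This is a one-sided worst case, because every exclusion falls in the test arm. It shows how the bias works and does not estimate what would happen in this trial.

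**The case against.** The best defence is that 5.5 does not mean removal from the FAS. The heading of section 4.8 joins dropouts and excluded cases, so 5.5 could point to the whole of 4.8. In that case 4.8.2 would keep these subjects in the full data set. Or 5.5 could mean PPS removal only, which fits the PPS definition in 10.1. Analysis sets are defined in section 10, not in the dosing section, and the English is a rough translation. Both readings are possible, and they are why confidence is only medium. Neither is stated. Where the protocol means a dropout it uses a different term, as in 7.3 for unblinded subjects, while the wording of 5.5 matches the category in 4.8.3.

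A second defence is that the blind audit in 5.6 would settle set membership. That meeting has no stated rule that overrides 5.5. Blinding the decision also does not remove bias from an exclusion that treatment itself caused.

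A third is that few subjects are affected. This has weight. Section 5.5 itself forbids dose adjustment, and the usual responses to adverse events in 7.1.4 are to continue or discontinue the drug, with no dose change listed. The background section reports no recorded adverse reactions, which is weak evidence but the only indication of frequency.

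A reader might also infer that these subjects would vanish from the adverse-event rates. The documents do not support that: the SS rule in 10.1 keeps everyone treated at least once. The literal wording of 5.5 conflicts with that rule but does not displace it.

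**Conclusion.** Section 5.5 is wrong as written. Taken with 4.8.3, it makes a post-randomisation exclusion that can depend on treatment, on a ground missing from the protocol's own list. It conflicts with the FAS and SS definitions and with the handling of withdrawals. Confidence is medium because the wording is ambiguous and may have been meant for the PPS alone.

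The effect on the primary comparison cannot be computed from the document. It is zero if excluded subjects respond at their arm's overall rate, and about 1 to 4 points in favour of the test drug if 2 to 8 test and 1 to 3 control non-responders, and no responders, are excluded. All of these counts are assumed. A reader might conclude that the rule would usually inflate the apparent benefit. That does not follow, because the direction depends on which arm has more dose changes and how those subjects fare, and the protocol informs neither.

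**What to change.** Reconcile 5.5 with 4.8.3 and 10.1 by replacing its reference to excluded cases. The new sentence should say that subjects whose dose or administration changes, for adverse events or any other reason, stay in the FAS and SS in their randomised arm. The change is recorded as a protocol deviation that can affect at most PPS membership, decided at the blind review. Section 4.8.3 then remains the only list of exclusion grounds.

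The cost is one sentence in the protocol, with no additional data or subjects. The change concerns analysis-set membership only and proposes no dosing rule.

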5.6 Blind method

A double blind design was used in this study.

(1) Generation of processing codes

Randomization method was used. They are carried out according to the center. With the help of SAS 9.1.3 statistical software, the random arrangement (i.e. random coding table) of the treatment (test drug and control drug) received by 240 subjects

was generated.

(2) Drug preparation

Firstly, random sampling of the drugs prepared by the applicant (test drugs and control drugs) is conducted to provide the corresponding drug inspection report. Secondly, the bidders will package the drugs according to the requirements of drug packaging.

(3) Preparing for Emergency Letters

1) Emergency letters, drug numbers and blindness regulations of Xinnaoning Capsule in the clinical study of chronic stable angina pectoris are printed on the sealed opaque envelope. If it is disassembled, it is necessary to specify the disassembler, the date of disassembly, the reason and so on, and record it in the case report form.

2) The envelope contains the information of the patient's medication and the address of the unit and the address that should be reported immediately. After the preparation of the emergency letter, it will be sent to the centers along with the drugs, which will be recovered after the study.

(4) Packaging and numbering of drugs according to processing codes

Personnel unrelated to clinical observation, surveillance and statistical analysis of this clinical study will attach the corresponding drug number to the conspicuous position of the external packaging of the drug according to the established processing code.

(5) Processing Blind Records of Coding and Drug Packing

The whole drug coding process is written into a document form by the blind person, that is, a blind record, which is kept as one of the documents of the clinical research. Its contents include: preparation of bidders' medicines, packaging, usage, storage requirements, methods of drug distribution, generation of random processing codes, packaging of medicines according to each subject, emergency letters, inspection reports of test drugs and control drugs, preservation of blind bases, provisions for eliminating blindness and distribution of the number of medicines in each center, etc.

(6) Distribution of packaged drugs

Emergency letters with separate packages of research drugs and corresponding drug numbers are sent to the research centers according to random central numbers.

(7) Blind bottom preservation

All the blind bases formed by coding, together with the initial values of random numbers and the length of blocks, are sealed and handed over to the drug clinical research institutes and bidders of Xiyuan Hospital, Chinese Academy of Medical

Sciences, respectively, for proper preservation. During the research period, the blind bases are not to be dismantled. The study will be considered invalid if any non-prescribed blind bottom leak occurs and affects the objectivity of the results of the study.

(8) Blind Audit and Disclosure Provisions

Blind auditing refers to checking and evaluating the data of the database after the last medical record report form is input into the database until the first blindness is uncovered.

When all the case reports are entered in two copies and checked correctly, the data manager writes out the database inspection report, which includes the completion of the study (including the list of dropped subjects), selection/exclusion criteria, integrity check, logical consistency check, outlier data check, time window check, combined drug use check, adverse event check and so on.

At the blind auditing meeting, the main researchers, bidders, supervisors, data managers and biostatistics professionals will examine the subjects' signing of informed consent, the situation of maintaining the blindness in the research process and the emergency situation of eliminating the blindness in the research process, and make decisions on the issues raised in the database inspection report, and write the blind auditing report. The database will be locked at the same time.

After data locking, the first blindness was uncovered by the staff who kept the blind bottom. This blindness uncovering only listed the group code of each subject (such as the experimental group or the control group). It was input to the computer by the statistic analyst and linked to the data file for statistical analysis. When the statistical analysis is finished, the statistical analysis report is written. At the summary meeting, the second blindness was uncovered. This blindness uncovering marked the actual corresponding groups of A and control group (such as experimental group or control group).

(9) Regulations on Emergency Disclosure of Blindness

When an emergency (such as a serious adverse event) occurs or the patient needs to know what kind of treatment the patient receives, the researcher immediately notifies the main researcher, urgently opens the emergency letter, and promptly notifies the head of the base and the inspector of the unit. Once the emergency letter is opened, the numbered subjects will withdraw from the study. Researchers should record the causes in the case report form, and record the time, place and cause of emergency blindness on the emergency letter. At least two people should sign it. At the end of the study, the case report forms were retrieved together for blind review after the study.

(10) Failure of double-blind study stipulates that the rate of blind bottom leak or emergency letter open exceeds 20%.

5.7 Drug Distribution and Preservation

Drug administrators (centers, according to their own management system, set up a special person responsible for the preservation, distribution, recovery, recording and return or recovery of experimental drugs) distribute drugs according to the order of the selected time and the number of drugs from small to large, and then withdraw the surplus experimental drugs after stopping the drugs, and fill in the Test Drug Use Record Form in time, which includes: The date of drug release, the name of the subject, the quantity of drug delivery, the date of drug recovery, the quantity of drug recovery, the signature of the dispenser and the signature of the drug collector, etc. After the completion of all trials, the drug administrator is responsible for returning the remaining drugs to the applicant or destroying them according to the procedure (filling in the "Test Drug Return/Destruction Certificate") and submitting them to the clinical trial unit for archiving.

During the test period, a management system should be established for the trial period of the test drugs, and special cabinets should be set up to keep the test drugs and store them in places where ventilation, drying and temperature are suitable. The drug administrator shall carry out unified management.

